5.14. Follow-Up Visit Study Procedures: Month 18 (\pm 7 days)

1. Medical History
2. Physical Examination
3. Peripheral Vascular Intervention Update
4. Assessment of CLI (associated measurements are listed separately)
5. Ulcer/gangrene and Index Leg Photography (after debridement, if necessary)
6. Retinopathy Examination
7. Hemodynamic Measurements
8. QOL Measurements (VascuQol Questionnaire)

9. Ischemic Rest Pain severity measured using the VAS pain scale (see Appendix E)
10. Collect Laboratory Test samples for the following: Hematology, Chemistry, CBC, Urinalysis, and an anti-HGF antibody
11. Adverse Event review
12. Concomitant Medication review
13. Weight and Vital Signs assessment

5.15. Assessments to Complete Prior to a Planned Intervention (Surgical Revascularization or Major Amputation)

1. Details of planned Intervention (type, date, etc)
2. Assessment of CLI (associated measurements are listed separately)
3. Ulcer/gangrene Photographs of Index Leg (after debridement)
4. Angiogram Assessment
5. Hemodynamic Measurements
6. QOL assessment using VascuQol Questionnaire
7. Ischemic Rest Pain severity measured using the VAS pain scale
8. Adverse Event review
9. Concomitant Medication review
10. Weight and Vital Signs assessment

5.16. Interim Telephone Contacts

The data collected during the entire study period are critical for the safety and efficacy assessments. Every effort will be made to bring the subject back to the study site for all scheduled visits. Due to the long time period between the Month 6 and Month 9 visits and the Month 15 and Month 18 visits, Study Personnel must make and document a telephone contact with each subject at Month 7.5 (\pm 5 days) as well as at Month 16.5 (\pm 5 days).

5.17. Unscheduled Visits

If the site is notified (e.g., at an Interim Telephone Contact) that the subject has experienced an AE that appears to be serious (see Section 8.2.2) or a significant deterioration in CLI status an attempt will be made to evaluate the subject at an unscheduled visit by the study staff unless the subject has been hospitalized remotely. If the subject has been hospitalized remotely details of the illness and treatment will be obtained and documented in the CRF.

Subjects who require 2-week confirmation of largest ulcer healing should also be evaluated at an unscheduled study visit by the study staff.

Data from unscheduled clinic visits will be collected in the CRF.

5.18. Ulcer Healing

Ulcer healing of the largest ulcer on the index limb (determined at Screening) will be assessed clinically by the Principal Investigator by direct visual inspection at each study visit. If the largest ulcer on the index leg is considered completely healed, photographs of the healed ulcer area must be captured. If the ulcer heals completely during the study period, the ulcer must be re-evaluated 2 weeks after healing to confirm it has remained healed for a period of 2 weeks. Confirmation of complete ulcer healing must be made by an outside physician unconnected with the study and nominated for this purpose

5.19. Diabetic control

Every effort will be made to ensure good diabetic control ($\text{HbA1c} \leq 7\%$), which will not only include maintaining ideal blood glucose levels, and appropriate foot care, but also managing diabetic complications such as diabetic retinopathy, neuropathy, and nephropathy. Ideally diabetic subjects should have their diabetes managed by a diabetic specialist (endocrinologist) throughout their participation in the study.

5.20. Documentation of Deaths

In cases where death is the outcome of a Serious Adverse Event (SAE), or occurs suddenly without apparent cause, appropriate documentation will be requested by the Sponsor.

All deaths including cases where death is due to subjects' worsening CLI, must be supported by source documentation such as a hospital discharge summary, death certificate, autopsy report or a doctor's report/letter. All serious adverse events with the outcome of death will be reported **immediately** to the Sponsor on the CRF via email or fax.

6. SCREEN FAILURES AND SUBJECT WITHDRAWALS

6.1. Withdrawals

A subject may refuse any or all treatment or study procedures at any time during the study. Participation is voluntary, and refusal to participate will involve no penalty or loss of benefits to which the subject is otherwise entitled. *A subject who refuses to participate after receiving one or more doses of the study product should be encouraged to continue follow-up as per protocol including the safety follow-up program (See Section 10) Safety Follow-up Program regarding safety follow-up procedures).*

If the subject wishes to withdraw study consent, every effort must be made to encourage the subject to return to the study site for safety evaluation purposes for all remaining study visits. Subjects who wish to withdraw from the study prematurely and have had at least one dose of study product will be requested to return to the study site for study specific safety and efficacy assessments.

If the subject withdraws prior to Month 6, the procedures for the Month 6 visit should be completed as the exit visit. If the subject withdraws between Month 6 and Month 18, the procedures for the Month 18 visit should be completed as the exit visit. Additionally, every effort will be made to obtain and record information regarding revascularization by surgery, major

amputation, myocardial infarction, stroke, and death even if the subject does not return for an exit visit. In case any of these events have occurred, evidence from source documents will be obtained for confirmation. Prior informed consent will have been obtained from the subject to gain access to these documents. If the subject refuses any continued study participation, decline of study participation should be documented in writing. If the subject refuses to communicate with the study site, final attempts to contact the subject should be documented with a certified letter to the subject's last known address.

The Principal Investigator is permitted to discontinue the subject from receiving study product for medical reasons at any time. However, the subject will continue to return for protocol dictated follow-up visits for the remainder of the total study period (18 month visit) including the safety follow-up program.

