4.7. Peripheral Vascular Intervention History (or Update)

During Screening

At Screening, the Investigator will perform a detailed assessment of all past peripheral vascular interventions (surgical bypass, an endovascular intervention or major/minor amputations). If the subject has never undergone a peripheral vascular intervention then the lack of these events will be documented as well. Information may include: date(s) of intervention, type(s) of intervention (e.g., PTA, surgical bypass, amputation, etc.), intervention site (e.g., iliac, femoro-popliteal, infrapopliteal, etc.), intervention side (right or left leg and index or non-index leg) conduit used (e.g., saphenous vein, polytetrafluoroethylene [PTFE], human umbilical vein [HUV], Dacron, etc.), and patency of most recent intervention prior to study start (including a description of the results from the most recent vascular imaging if available). Information concerning both major (defined as at or above the ankle) and minor (below the ankle) amputation should be collected. Specific information for each peripheral vascular procedure will be obtained and recorded on the

subjects' source documentation and CRF to allow independent review of the subjects' CLI status and suitability for entry into the study.

During Treatment and Follow up Period

During the study, detailed information must be documented in the subjects' source documentation and CRF on the subject's CLI status of the index leg including any treatment received for worsening CLI of the index leg, plan for major or minor amputations of the index leg, plan for revascularization procedures of the index leg, etc. Detailed information on the subjects' CLI status must be documented prior to planning a surgical revascularization or major amputation of the index leg. Data relating to the reasons for performing a surgical revascularization or major amputation of the index leg will be reviewed.

In no way will intervention that is deemed necessary be withheld for any subject.

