
(6) Photos of largest ulcer on the index leg as well as a photo or photos (if necessary) of the entire index leg to show all ulcer/gangrene locations. Debridement should be performed prior to these evaluations;

(7) Procedure must be performed prior to a planned interventional treatment (revascularization or amputation) while on study.

** For the purposes of this study a month is defined as 30 days. Days 14, 28 and 42 are calculated from either Day 0, Month 3, Month 9 or Month 12. All (non-dosing) follow-up visits should be calculated based on Day 0/Baseline.

Table 4: Schedule of Sample Collection for the Serum HGF Protein & PCR for HGF Plasmid Assays

Schedule of Sample Collection for the Serum HGF protein & PCR for HGF Plasmid Assays																	
PROCEDURE	Dosing Visit: First Cycle	PK Sampling Visit	Dosing Visits: First Cycle							Follow Up Visit	Dosing Visits: Second Cycle				PK Sampling Visit	Dosing Visit: Second Cycle	Follow Up Visit
Time	Day 0	Day 4	Day 14	Day 28	Day 42	Month 3	Month 3 Visit + 14 Days	Month 3 Visit + 28 Days	Month 3 Visit + 42 Days	Month 6	Month 9	Month 9 Visit + 42 Days	Month 12	Month 12 Visit + 4 days	Month 12 Visit + 42 Days	Month 15	
Vist Window	Baseline	0	± 2 days	± 2 days	± 3 days	± 7 days	± 2 days	± 2 days	± 2 days	± 7 days	± 7 days	± 2 days	± 7 days	0	± 2 days	± 7 days	
Serum HGF protein Assay	X*	X	X*	X*	X*	X*			X*		X*		X*	X			X
PCR for HGF plasmid DNA Assay	X*	X	X*	X*	X*	X*	X*	X*	X*	X	X*	X*	X*	X	X*	X*	X

*At Dosing Visits (indicated by the shaded columns), two (2) samples should be drawn one pre-dose and a second drawn four hours post-dosing.

** The first 5 subjects who were randomized and received test medication will have blood samples drawn for PK 4 days following their Month 9 Visit.

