9. EVALUATIONS AND STATISTICAL METHODS

9.1. Evaluations

The following evaluations relating to tolerability, safety and clinical benefit will be made:

1. Adverse events (AEs) suspected to be related to injections of HGF plasmid
2. Discontinuations related to adverse effects from the injections of HGF plasmid
3. All AEs up to Month 3, Month 6, Month 12, and Month 18
4. Serious adverse events (SAEs) up to Month 3, Month 6, Month 12, and Month 18
5. Number of deaths and cause over the 18 month period up to Month 3, Month 6, Month 12, and Month 18
6. Number of subjects in whom the largest ulcer healed completely or gets smaller (photo confirmation) at 6, 12 and 18 months (cumulative)
7. Number of subjects in whom rest pain (based on the 100 mm VAS scale) reduces by 20 mm or more or was completely relieved at 6, 12 and 18 months (cumulative)
8. Change in VascuQol Questionnaire (QOL) score compared to the baseline at 6, 12 and 18 months
9. Number of subjects revascularized (bypass or endovascular intervention) up to Month 3, Month 6, Month 12, and Month 18
10. Number of subjects with minor and number of subjects with major amputations (at or above the ankle) up to Month 3, Month 6, Month 12, and Month 18

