10. SAFETY FOLLOW-UP PROGRAM

Since this study uses a DNA plasmid for gene transfer, the Sponsor (AnGes, Inc.) is complying with regulatory guidance to conduct long-term safety follow-up to collect safety information on all participants who receive the study product. The long-term safety follow-up data will be collected every 6 months for an additional 18 months following the Month 18 Visit.

Adverse Events should be documented and followed from the start of the first dose of study product (Day 0), until the final outcome is known or until the end of the study safety follow-up period. AEs (including SAEs) that have not resolved by the end of the study follow-up period should be recorded in the CRF as "ongoing". If it is not possible to obtain a final outcome for a SAE, the reason that a final outcome could not be obtained must be documented (e.g., completion of follow up, subject has moved and cannot be contacted, etc.). Serious Adverse Events should be reported within 24 hours of site awareness.

Deaths, major amputations, revascularizations by surgical bypass, stroke, and myocardial infarction will be source verified. An appropriate request/permission for this safety follow-up program will be included in the informed consent.

The data collected during the follow-up period will consist of surgical revascularization, lower limb amputation, cancers, eyesight changes, bleeding/blood disorders, autoimmune diseases, neurological disorders, hospitalizations, unexpected or significant illnesses including stroke, myocardial infarction, and death. In the event of death, information regarding the above data (as best as possible) and date and cause of death will be requested from a spouse or nearest relative. The questionnaire is found in Appendix F.

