2.5.5 Efficacy Analysis

- Ulcer improvement**

A table showing the number of subjects completely healed in the target ulcer will be provided at up to 6 months, > 6 months to 12 months, from >12 months to 18 months. If available, the number of subjects with at least 20% reduction in bi-dimensional size (by measuring largest diameters) will be provided. The reduction in bi-dimensional size will be calculated by taking the product of the largest diameters for each baseline and postbaseline measurement, then subtracting the baseline result from the postbaseline result.

- Ischemic Rest pain (of the index leg) using a 10 cm VAS scale**

Rest pain severity will be assessed at the specified predetermined time points. Rest pain severity will also be assessed prior to surgical revascularization or major amputation (of the index leg). A table showing the number of subjects reduced by ≥ 20 mm from baseline in VAS score will be provided at up to 6 months, > 6 months to 12 months, from >12 months to 18 months. Summary statistics will be provided for baseline and change from baseline for each visit and LOCF. One sample t-test for change-from-baseline will be performed. If death occurs, the worst score prior to death instead of last observation will be carried forward.

- Hemodynamic Measurements**

Summary statistics will be provided for baseline and change from baseline for hemodynamic parameters (right/left brachial systolic pressure, ankle systolic pressure measured at dorsalis pedis and posterior tibial, toe systolic pressure, calculated ABI, and calculated TBI) by visit. At each visit, only subjects who have a non-missing value at both baseline and the specific visit will be summarized. Two-sided one-sample t-test will be performed for each visit and LOCF.

- Subjects with any worsening CLI event of index leg**

A summary table and listing of worsening CLI-related events of the index leg including any new or worsening events, worsening rest pain, new ulcer or worsening ulcer, new or worsening wound infection, peripheral vascular intervention, complication of a peripheral vascular intervention, cellulitis, and amputation due to worsening CLI will be provided.

- Subjects who either died, had MI, Stroke, revascularization (by surgical bypass, by endovascular intervention, by hybrid procedure), major amputation, or all-cause death**

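### Endovascular revascularization is a counted outcome, but the event search after withdrawal names only surgery, and the documents conflict on which revascularizations need pre-procedure assessments

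*Protocol*

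**What the plan says.** **What is counted.** Protocol 9.1 item 9 lists "Number of subjects revascularized (bypass or endovascular intervention) up to Month 3, Month 6, Month 12, and Month 18". The event table in SAP 2.5.5 covers "revascularization (by surgical bypass, by endovascular intervention, by hybrid procedure), major amputation, or all-cause death", besides myocardial infarction and stroke.

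**What is sought after withdrawal.** Protocol 6.1 asks withdrawing subjects to complete the Month 6 or Month 18 procedures as an exit visit. If a subject does not return, "every effort will be made to obtain and record information regarding revascularization by surgery", together with major amputation, myocardial infarction, stroke and death. Events found this way are to be confirmed from source documents.

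**What is assessed before a procedure.** Protocol 5.15 is headed "Assessments to Complete Prior to a Planned Intervention (Surgical Revascularization or Major Amputation". It lists CLI status, photographs, angiogram, hemodynamics, VascuQol and VAS, among other items. Protocol 4.7 says that detailed CLI status "must be documented prior to planning a surgical revascularization or major amputation of the index leg". Footnote 7 to protocol Table 3 is wider: "Procedure must be performed prior to a planned interventional treatment (revascularization or amputation) while on study". The SAP schedule repeats that footnote, and protocol 4.11 requires a VAS score before any planned revascularization or major amputation.

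**What the analysis uses.** SAP 2.4.2 replaces VAS data after revascularization of any type, or after major amputation, with the last available value before the intervention.

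**The concern.** The outcome is defined more widely than the rule for finding it in subjects who leave. A count is only as complete as its search. The search in 6.1 is the one that applies when a subject is no longer seen, and it omits a type of procedure that both documents count. Leaving and being revascularized may also be linked: SAP 2.5.7 plans a table that includes subjects who discontinued because of revascularization.

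The second issue is a contradiction. VAS handling in the SAP depends on a measurement shortly before any revascularization. The operational checklist in 5.15 asks for one only before surgery or major amputation, while the schedule footnote and 4.11 ask more widely. Two sites reading different sections would behave differently. Because feasibility of the study activities is a primary objective of this pilot for the phase 3 trial, conflicting instructions of this kind bear on what it is meant to test.

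**Working it through.** The documents give no event rate or sample-size calculation for this point, so the check is a comparison of texts plus two small sums.

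**Step 1. Set the passages side by side.**

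| Topic | Surgical wording only | Wider wording |
|---|---|---|
| Outcome counted to Month 18 | none | Protocol 9.1 item 9; SAP 2.5.5 |
| Recording while the subject attends | Protocol 4.9 names bypass, but its list is open-ended | Protocol 4.7 (treatment for worsening CLI, plans for revascularization); intervention update at every clinic visit in Table 3 |
| Search after withdrawal without an exit visit | Protocol 6.1 | none found |
| Assessments before a procedure | Protocol 5.15; 4.6 (angiogram); 4.7 (CLI status); 4.9 (photographs); SAP 2.5.5 (rest pain) | Protocol Table 3 footnote 7; SAP schedule footnote 7; Protocol 4.11 (VAS) |
| After Month 18 | Protocol 10 data list and source verification | Protocol 10, later list (index limb); Appendix F question 11 |

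**Step 2. Locate the counting gap.** In the third row, nothing offsets the narrow wording. Adverse event forms are not a dependable backstop, because protocol 8.1.1 and 8.1.2 generally keep worsening CLI of the index limb off them. For subjects who attend, the intervention update captures endovascular procedures. It is also part of the Month 6 and Month 18 lists used as exit visits (5.7 and 5.14).

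**Step 3. Size of one missed event.** The weight of one subject is 1/N, with N = 8 to 10 (protocol section 3):

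- N = 10: 1/10 = 10.0 percentage points
- N = 8: 1/8 = 12.5 percentage points

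This is the effect of one event, not an estimate of how likely it is. Subjects enter with no endovascular option (protocol 3.1), so few are expected.

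**Step 4. Age of the carried-forward VAS.** A month is 30 days in this protocol. No clinic visit lies between Months 6 and 9 or between Months 15 and 18, and each of these visits has a window of ±7 days:

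- nominal gap: 3 × 30 = 90 days
- widest gap: 90 + 7 + 7 = 104 days

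If a planned endovascular procedure falls at the end of such a gap and the site follows 5.15, the value used under SAP 2.4.2 could be that old. Similar gaps could arise in the dosing quarters. Protocol 4.11 asks for VAS at all visits, but the lists for the +14, +28 and +42 day visits (5.5, 5.6.2 and 5.9) omit it.

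**Step 5. Which assessments are in conflict.** For VAS, both 4.11 and footnote 7 stand against 5.15. For VascuQol, hemodynamics and photographs before an endovascular procedure, footnote 7 is the only wider text. The scope for amputation differs too: footnote 7 has no limit, whereas 5.15 and 4.11 say major.

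**The case against.** The best case on the other side is that this is minor wording in a descriptive, single-arm pilot, and that much of the protocol is wider than 6.1 and 5.15 suggest. Several stronger readings are tempting, and the documents do not support them.

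- **That 4.7, 4.9 and section 10 cover only surgery.** Section 4.7 counts endovascular procedures among peripheral vascular interventions and requires revascularization plans to be recorded. The status list in 4.9 is open-ended. Section 10 goes on to mention revascularization of the index limb without limit, and question 11 of its questionnaire asks about any revascularization procedure.
- **That endovascular events can be missed in general.** Subjects who attend are covered by the update at each visit.
- **That the source-verification sentence in section 10 ("Deaths, major amputations, revascularizations by surgical bypass, stroke, and myocardial infarction will be source verified") lowers the outcome counts.** That programme starts after Month 18, where the counts end.
- **That pre-procedure assessments are simply not required before an endovascular procedure.** Footnote 7 and 4.11 require them. The fault is a contradiction, and an old VAS arises only if a site follows 5.15 instead.
- **That the errors favour the product.** A missed event lowers the count, but there is no comparison arm, and it is an assumption that an older VAS would be lower than the one just before the procedure.

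These points narrow the issue. They leave standing the surgical limit in 6.1, which no other passage widens, and the conflict over pre-procedure assessments.

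**Conclusion.** The point holds in two limited parts.

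1. **Counting.** An endovascular or hybrid revascularization in a subject who withdraws without an exit visit lies outside the stated search and source confirmation, although both documents count it. One such event is worth 10 to 12.5 percentage points. The size assumes 8 to 10 subjects in the denominator; the frequency is unknown and probably low. The Kaplan-Meier analysis of major amputation or death is unaffected, because revascularization is not an event in it.
2. **Assessments.** Protocol 5.15, 4.6, one sentence of 4.7 and the photograph rule in 4.9 conflict with Table 3 footnote 7, SAP schedule footnote 7 and protocol 4.11. The consequence for the analysis is a carried-forward VAS that could be about 90 days old, and at most 104 days across the two longest intervals. That rests on a site following 5.15 and on visits falling within their windows.

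No pervasive omission and no demonstrated bias follow from the documents. The correction is worthwhile because it is cheap and closes a gap in a listed outcome.

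**What to change.** 1. In protocol 6.1, replace the surgical wording with *revascularization (surgical bypass, endovascular or hybrid)*. Do not add an index-leg limit: neither 6.1, nor 9.1 item 9, nor the SAP event table has one, so adding it would drop non-index-leg surgery from the search while the outcomes still count it.
2. Use the same definition in the section 10 data list and source-verification sentence. This is for consistency and affects only data after Month 18.
3. Reconcile protocol 5.15, 4.6, 4.7 and 4.9 with Table 3 footnote 7 and 4.11, so that the documents state one rule on which planned revascularizations and amputations need the prior VAS, VascuQol, hemodynamics and photographs. Align the rest-pain sentence in SAP 2.5.5 with that rule. The sponsor must settle its scope, including the angiogram; for the analysis, SAP 2.4.2 relies on a VAS value before any revascularization.
4. State in the SAP that a pre-procedure VAS is eligible for carry-forward. SAP 2.4.3 excludes unscheduled measurements, and a pre-procedure assessment could be read as one.

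The cost is protocol and SAP wording, a few more records to confirm from source, and a few pre-procedure assessments that footnote 7 already calls for.
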